Product that will be given to participants for the Baseline 2 visit cannot be given/sent to participants until 7 days have passed following completion of the Baseline 1 visit. We will need to calculate baseline smoking rate during this 7-day period and so participants cannot have access to any study product before this 7-day period has ended.

Visit scheduling requirements for baseline period:

Participants will be required to schedule the Baseline 1 visit within 30 days of the completion of their screening visit. If a participant still wants to be in the study after 30 days, she will need to be re-screened. The participant will need to be re-consented but will maintain the original REDCap Subject Identifier. The ideal target window separating Baseline 1 and Baseline 2 is between 7 and 12 days. The minimum is 7 days and the maximum is 21 days. If the participant does not complete the visit within 21 days, then she will not be rescheduled and will be discontinued from the study.

Measures/Assessments

The following physiological measures will be collected at Baseline 1 and recorded directly into REDCap by the interviewer:

- 1) CO
- 2) Blood pressure
- 3) Heart rate

The following assessments will be administered as an interview at Baseline 1 and entered directly into REDCap by the interviewer:

- 1) Concomitant Medications Form
- 2) Time Since Last Cigarette Questionnaire
- 3) Health Changes Questionnaire, which will assess any weekly health changes
- 4) Maintenance Drug Dose Questionnaire (if applicable)

The following assessments will be administered at Baseline 1 and completed by the participant directly in REDCap:

- 1) BDI
- 2) OASIS
- 3) Perceived Health Risks Rating (Hatsukami et al., 2010), a measure of the perceived addictive potential and other health risks associated with cigarettes
- 4) Respiratory Health Questionnaire, a measure of cough, shortness of breath and other respiratory symptoms
- 5) Minnesota Nicotine Withdrawal Scale (MNWS; Hughes & Hatsukami, 1986), a measure of nicotine withdrawal
- 6) Questionnaire of Smoking Urges-brief scale - Usual Cigarette (QSU-brief; Cox, Tiffany, & Christen, 2001; Tiffany & Drobes, 1991), which measures the urge to smoke
- 7) Cigarette Evaluation Scale – Usual Cigarette (CES; Westman, Levin, & Rose, 1992), which measures responses to cigarettes (e.g., reward, satisfaction)

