The following assessments will be administered as an interview and will be entered directly into REDCap by the interviewer:

- 1) Concomitant Medications Form
- 2) Time Since Last Cigarette Questionnaire
- 3) Health Changes Questionnaire
- 4) Medical Event Form (if applicable)
- 5) Maintenance Drug Dose Questionnaire (if applicable)

The following assessments will be completed by the participant directly in REDCap:

- 1) BDI
- 2) OASIS
- 3) MNWS
- 4) QSU brief – with reference to assigned cigarette
- 5) CES – with reference to assigned cigarette
- 6) PUQE-24
- 7) COVID-19 Symptom Questionnaire

In the event that the REDCap website is not functioning, the assessments will be administered aloud and participant answers will be recorded securely. The interviewer will enter the data into REDCap when it resumes functioning properly. A note indicating that REDCap was not functioning during the session should be recorded in the 'End of Visit Evaluation Form'.

Experimental Visits: Study Weeks 2, 4, 6, 8, 10 & 12:

Measures/Assessments

Physiological measures will be collected and entered directly into REDCap by interviewer:

- 1) CO
- 2) Blood pressure
- 3) Heart rate

The following assessments will be administered as an interview and will be directly entered into REDCap by the interviewer:

- 1) Concomitant Medications Form
- 2) Time Since Last Cigarette Questionnaire
- 3) Health Changes Questionnaire
- 4) Medical Event Form (if applicable)
- 5) Maintenance Drug Dose Questionnaire (if applicable)

The following assessments will be completed by the participant directly in REDCap:

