- If the participant chooses not to receive the study product, have her contact the lab if she lapses and would like to pick up or be mailed the study product prior to her next visit.

If a Participant is Planning to Quit Smoking, but has not initiated the quit attempt:

- Ask if she has identified a target quit date and, if so, what that target date is
- Provide the participant with the '*Clearing the Air*' manual and local smoking cessation resources
- Provide the participant with the study product as usual. Recommend that on the target date she put the product "away" at home as to avoid unwanted cues to smoke.

Abstinence Assessment Session:

After the week 12 visit, participants will be required to attend one additional visit the following day. Participants will have been encouraged to abstain from smoking leading up to this visit. The abstinence assessment session should be scheduled no less than 18 hours and no more than 30 hours after the Week 12 visit. Abstinence will be verified by CO levels that have decreased by at least 50% from the measure taken during the Week 12 visit. This session will allow us to determine whether the experimental cigarettes have reduced the effects of abstinence on these measures relative to the control conditions. If the participant does NOT meet abstinence criteria, she will only receive \$20 for the visit.

Measures/Assessments

Physiological measures will be collected and entered into REDCap by the interviewer:

- 1) CO
- 2) Blood pressure
- 3) Heart rate

The following assessments will be administered as an interview and will be entered directly into REDCap by the interviewer:

- 1) Concomitant Medications Form
- 2) Health Changes Questionnaire
- 3) Time Since Last Cigarette Questionnaire
- 4) Medical Event Form (if applicable)
- 5) Maintenance Drug Dose Questionnaire (if applicable)

The following assessments will be completed by the participant directly in REDCap:

- 1) BDI
- 2) OASIS
- 3) MNWS
- 4) QSU-brief – with reference to assigned cigarette
- 5) CPT - with reference to assigned cigarette
- 6) CES – Usual Brand Cigarette Version
- 7) COVID-19 Symptom Questionnaire

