## **3. Trial Objectives**

The primary objective of this study is to evaluate the effects of extended exposure to VLNC cigarettes in socioeconomically disadvantaged pregnant women. Parallel studies have been conducted with socioeconomically disadvantaged women of reproductive age, opioid-maintained smokers, and smokers with affective disorders. The study will use a two-condition, parallel-groups design. After a baseline period in which daily smoking rate and other baseline characteristics are assessed, participants will be randomly assigned to one of two cigarette conditions for the 12-week experimental period, namely VLNC cigarettes (0.4 mg/g tobacco) or each participant's reported usual brand (UB).

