## 6. Trial Endpoints

### 6.1. Primary Endpoints

The Primary Aim of the extended exposure study is to compare the effects of cigarettes varying in nicotine yield on smoking rate. The primary endpoint is average CPD during Week 12. Additional measures addressing this aim are breath CO level, urinary cotinine concentration, nicotine dependence (Fagerström Test for Nicotine Dependence, Wisconsin Index of Smoking Dependence Motives) scores, nicotine withdrawal (Minnesota Nicotine Withdrawal Scale, Questionnaire of Smoking Urges), and the Cigarette Purchase Task (CPT).

- CPD will be collected by daily Interactive Voice Response (IVR) to assess cigarette use in the days since the last interview. This will yield a continuous record of cigarette use throughout the study. A weekly average will be obtained for analysis by averaging the daily CPD reports.
- Breath CO
  - Collected at baseline and weekly for the duration of the study
- Urinary cotinine concentration
  - Collected at the second baseline, Weeks 6 and 12
- Nicotine dependence and withdrawal
  - Collected at screening, the first baseline, every other week (even weeks for nicotine dependence, odd weeks for nicotine withdrawal) until study completion and the abstinence visit
- CPT
  - Collected at the second baseline and Weeks 2, 6, 12 and the abstinence visit for usual brand cigarette
  - Collected at Weeks 2, 6, and 12 and the abstinence visit for study cigarette
  - Breakpoint: the lowest price at which cigarette consumption is 0.
  - Elasticity of demand: the sensitivity of cigarette consumption to price increases.
  - Omax: the maximum daily expenditure for cigarettes.
  - Pmax: the price at which cigarette expenditure is maximized.
  - Intensity: cigarette consumption at the lowest price (\$0 cost).

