## **7.3. Primary Endpoint Analysis**

### **7.3.1. Primary Analysis**

The primary endpoint is CPD during Week 12, compared to the CPD at baseline. While the primary outcome is the mean total CPD, consisting of both study and non-study cigarettes, the analyses will be repeated examining only the CPD contributed by study cigarettes. CPD will be computed as the mean CPD calculated on a weekly basis. Data analysis will use repeated measures analysis of variance, with two conditions and two time points (baseline and Week 12). In addition, the analysis model will include a random effect for site, a random

participant effect and random error (within-subject error). Variance parameters will be estimated using restricted maximum likelihood method with the Satterthwaite approximation.

Because CPD will be measured weekly, additional analyses will be performed including data collected at all time points. The analysis will be conducted in a manner similar to that described above, with the exception that there will be 13 time points: baseline and Weeks 1 through 12. For these analyses, the variance-covariance structure will be specified as first-order autoregressive.

Additional outcomes include the CPT, breath CO level, urinary cotinine concentration, and nicotine dependence and withdrawal scores. These will be examined in a manner similar to that described above for CPD. Natural log transformations will be performed as needed so that ANOVA model assumptions of normality and equal variances hold. Geometric means in original units will be calculated as well. Note that not all outcomes are assessed at weekly in-person visits. The time points at which each outcome is assessed is described in Section 6.

Finally, several assessments will be made at baseline as well as at the abstinence visit, which occurs the day following the Week 12 assessment. At this visit, measures of craving and withdrawal will be completed. The analysis will be similar to that described above for the CPD comparing baseline CPD to that reported at the end of the trial. The analysis will deviate from that described only in the timing of the tasks, with the time points consisting of the baseline and the abstinence visits, rather than the baseline and Week 12 visits reported above.

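### The QSU-brief asks about the usual cigarette at baseline and the assigned cigarette afterwards, so the planned craving contrast mixes any craving effect with a change of question in the VLNC arm only

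*Protocol*

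**What the plan says.** The Study 2 Baseline 1 list in the Protocol gives the scale as "Questionnaire of Smoking Urges-brief scale - Usual Cigarette". The list for Weeks 1, 3, 5, 7, 9 and 11 gives "QSU brief – with reference to assigned cigarette", and the Abstinence Assessment Session gives "QSU-brief – with reference to assigned cigarette". The even-week list, which includes Week 12, has no QSU-brief. No usual-cigarette version is listed after baseline.

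SAP section 3 defines the two conditions: "namely VLNC cigarettes (0.4 mg/g tobacco) or each participant's reported usual brand (UB"). The assigned cigarette is therefore the baseline cigarette in one arm and a different product in the other.

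SAP 6.1 places the scale among the additional measures for the primary aim, under "nicotine withdrawal (Minnesota Nicotine Withdrawal Scale, Questionnaire of Smoking Urges"). SAP 7.3.1 says of these outcomes: "These will be examined in a manner similar to that described above for CPD". For CPD that means a condition-by-time repeated measures model that includes baseline. For the abstinence visit SAP 7.3.1 adds: "At this visit, measures of craving and withdrawal will be completed", with baseline and the abstinence visit as the two time points. Neither document mentions the change in the cigarette asked about.

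**The concern.** A change-from-baseline comparison between arms needs the same question at both times, or at least the same change of question in both arms. Here the question changes after randomisation in one arm only, so randomisation does not balance it out. The condition-by-time term for the QSU-brief cannot separate two situations: VLNC women crave less, or they are being asked about a product they want less.

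This matters because the Protocol's background names severe craving and withdrawal with VLNC cigarettes as a possible harm in this population, and links it to compensatory smoking and use of other tobacco products. The abstinence visit is intended to show whether the experimental cigarettes reduce the effects of abstinence. If the change of question lowers scores, the QSU-brief would reassure on this point without cause.

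**Working it through.** **1. Which cigarette is asked about, by arm and visit**

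| Visit | Usual-brand arm | VLNC arm |
|---|---|---|
| Baseline 1 | usual | usual |
| Weeks 1, 3, 5, 7, 9, 11 | assigned = usual | assigned = VLNC |
| Even weeks, including Week 12 | not collected | not collected |
| Abstinence visit | assigned = usual | assigned = VLNC |

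The exposed contrasts are baseline versus odd weeks and baseline versus the abstinence visit. The baseline-versus-Week-12 comparison used for CPD does not exist for this scale.

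**2. What the contrast estimates**

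Let U0 and U1 be the urge for the usual cigarette at baseline and follow-up. For a VLNC woman at follow-up, let s be her urge for the VLNC cigarette minus her urge for the usual cigarette at that time. Her recorded follow-up score is U1 + s. Then

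contrast = [mean(U1 + s) − mean(U0)] in VLNC − [mean(U1) − mean(U0)] in usual brand = true difference in change + mean(s).

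The term mean(s) enters one for one. Dropping baseline does not remove it, because a comparison at follow-up alone still sets U1 + s against U1.

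**3. How large it could be**

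The plan gives no QSU figure to reproduce: no SD, no item wording, no power. The only Study 2 power statement (SAP 4.2, 45 completers per condition, 80%) is for CPD. What follows is an illustration.

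- Inputs from the SAP: n = 45 per arm, alpha = 0.05.
- Assumed: two-sided test, no true craving effect, and mean(s) equal in size to d SDs of the change score.
- Method: two-sample t, 88 df, critical value 1.987, noncentrality = d × √(45/2) = 4.743 × d.

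| d | noncentrality | probability of a significant result |
|---|---|---|
| 0 | 0 | 5.0% |
| 0.10 | 0.474 | 7.6% |
| 0.20 | 0.949 | 15.5% |
| 0.42 | 1.992 | 50.4% |
| 0.60 | 2.846 | 80.4% |

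**4. Sensitivity to the correlation**

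If the shift is expressed in SDs of the score itself, the SD of the change is √(2(1 − ρ)) times the score SD. A shift of 0.3 score SD is then 0.25, 0.30 or 0.39 change SDs at ρ = 0.3, 0.5 or 0.7. By the normal approximation, the rejection probabilities are 23%, 30% and 45%. With 53 per arm (half of the Protocol's randomisation target of 106) and ρ = 0.5, the figure is 34%.

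**5. Same question at every visit**

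If both arms are asked about the usual cigarette throughout, mean(s) drops out and the error rate returns to 5%.

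**The case against.** **Supporting measure.** The primary endpoint is CPD. The Protocol's Study 2 statistical section does not list the QSU-brief among the additional measures for the primary aim, and its outcome list puts it under secondary discomfort measures. This stands. A reader might infer that the main result is compromised; it is not, because CPD does not depend on this question.

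**Other measures cover craving and its consequences.** The MNWS is given at Baseline 1, at every odd week and at the abstinence visit, with no cigarette named. IVR withdrawal ratings run in the week before and the week after randomisation. SAP 6.1 lists a usual-brand CPT at Weeks 2, 6, 12 and the abstinence visit, although the Protocol's lists for those visits show only the assigned-cigarette version. Total CPD, breath CO and other nicotine use capture the feared consequences. This also stands, so it would be wrong to say that the plan has no sound measure in this area. However, the SAP does not say which scale prevails if the QSU-brief and MNWS disagree.

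**Direction.** A reader might infer that the bias must be reassuring, since the background reports a strong preference for the higher-dose cigarette. That finding comes from tests with both cigarettes on offer. The same paragraph reports that VLNC cigarettes, when they are the only ones available, are self-administered like normal ones. Study 2 women are supplied with one product and asked to refrain from others. Preference in a choice test is also not an urge score. A downward shift is plausible; the documents do not establish it.

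**Urge for the assigned product is a legitimate target.** For a nicotine-reduction policy it may well be. But then change from a usual-cigarette baseline is not a craving effect in the VLNC arm, and the SAP should not analyse or label it as one.

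**Conclusion.** The point holds as a limitation of one supporting measure. The change of question, its restriction to the VLNC arm and the planned use of baseline all follow from the text, and no provision deals with them. The QSU-brief contrasts at odd weeks and at the abstinence visit cannot be read as craving effects as planned.

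The direction and size of the distortion are unknown. The range of about 8% to 80% false significance rests wholly on assumed shifts of 0.1 to 0.6 SD of the change score, 45 per arm, a two-sided 5% test and no true effect. It shows what such shifts would do, not what will happen. The documents do not support saying that the trial will show a false fall in craving. The change should be made, but the primary analysis does not depend on it.

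**What to change.** **For visits still to come.** At Weeks 1, 3, 5, 7, 9 and 11 and at the abstinence visit, also give both arms the usual-cigarette QSU-brief used at baseline. State in SAP 7.3.1 that only this version enters the change-from-baseline craving contrast, and keep the assigned-cigarette version as a product rating. The form already exists, and the Protocol already uses a usual-brand version of the CES at the abstinence visit. The cost is one short form at seven visits, plus SAP wording.

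**For visits already collected.** State in the SAP that:
- the QSU-brief is reported as urge for the assigned product;
- it is not analysed as change from the usual-cigarette baseline;
- the craving and withdrawal conclusion rests on the MNWS, supported by the IVR withdrawal ratings and by the usual-brand CPT if it is collected as the SAP lists.

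This costs only SAP text, at the price of giving up a change-from-baseline craving result from this scale for those visits.

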1. BDI
2. OASIS
3. FTND
4. WISDM-brief
5. PSS-4
6. PANAS
7. PUQE-24
8. COVID-19 Symptom Questionnaire
9. Respiratory Health Questionnaire (Study Weeks 2, 6, and 12 only)
10. Perceived Health Risks Questionnaire (Study Weeks 2, 6, and 12 only)
11. CPT – with reference to assigned cigarette (Study Weeks 2, 6, and 12 only)
12. Smoking Stages of Change Algorithm and Contemplation Ladder (Week 12 only)

In the event that the REDCap website is not functioning, the assessments will be administered aloud and participant answers will be recorded securely. The interviewer will enter the data into REDCap when it resumes functioning properly. A note indicating that REDCap was not functioning during the session should be recorded in the 'End of Visit Evaluation Form'.

Biological Samples to be collected (Study Weeks 6 and 12 only):

- 1) First void urine sample

Interactive Voice Response System:

Participants will continue to use the IVR system on a daily basis throughout the experimental period to record the number of study cigarettes smoked per day and use of non-study cigarettes, if applicable. During the first week after Baseline 2 (randomization), the IVR system will collect information about withdrawal symptoms.

Variable Incentive Program:

An incentive program has been developed with the goal of improving attendance at scheduled assessment sessions and encouraging honest self-reports regarding all nicotine/tobacco use.

Briefly, participants will receive a total of five tickets for each visit they attend after randomization. Participants will be instructed that these tickets correspond to attendance (three tickets) and honest reporting (two tickets). They will be further instructed that these tickets "could" be eligible for entry into a monthly drawing for prizes, but that only tickets that are "validated" will be eligible for prizes.

Since it is prohibitively expensive to test urine samples each week for each participant and because it is currently not feasible to detect with reasonable precision non-compliance based on biomarkers in the higher nicotine group, we plan to only validate the attendance tickets. Hence, each participant who attends their regularly scheduled weekly session will have a total of five validated tickets entered into the monthly drawing.

To convey the message that we may be validating honest reporting and use of only study-provided products, in a bogus pipeline of sorts, we will tell the participants that a composite assessment of the measures that we collect MAY be used to validate the amount of nicotine and tobacco products that they are using. So there is some minor deception involved, but technically we could conduct urine

toxicology testing for both purposes. Hence, if the urine toxicology testing is presented as something that MAY be done for validation purposes, we feel that any deception is relatively minor. For scientific/economic reasons we are just electing to restrict validation to attendance. Nevertheless, we will debrief all participants upon the completion of the trial. We will inform them that the incentive program was based exclusively on attendance due to the relatively high cost of urine toxicology testing and other practical problems with shipping the urines for prompt testing.

Drawings will be conducted on the 1st of each month. Validation will be performed by staff who have no participant interaction and are not blind to condition. Any ticket drawn will be eligible for an incentive as the only true contingency is for attendance. There will be no mention of the basis for earning incentives (i.e., whether the ticket was for attendance, honesty, adherence,). Participants will simply be informed that he or she earned an incentive from the drawing.

Each drawing will be independent (without replacement); consequently, some participants will not win a prize and others may win more than one during the study if more than one of their tickets is drawn. After confirming winners, the remaining tickets from each month will be discarded (i.e., tickets will only be entered into one drawing). The monthly prize amounts are detailed below.

Grand Prize (1): \$500 cash
Second Prize (1): \$200 cash
Third Prize (5): \$10 cash

Product and Procedures Compliance Review Sessions:

At each visit, Baseline 2 through Week 12, participants will be counseled about their use of the study cigarettes, if applicable. Participants will be asked about any concerns or obstacles associated with use of the study cigarettes. The importance of honest self-reporting will be stressed. Participants will be told that they will not be penalized for use of other nicotine or tobacco products and that it is crucial for them to report any use of these products. If difficulties are encountered, participants will be asked why they think they are experiencing difficulties (e.g., taste, withdrawal symptoms) and to problem-solve how to deal with these difficulties in order to meet the protocol requirements. Additionally, participants will be counseled about their IVR completion, visit attendance, task engagement and product accountability. Refer to the '*Product and Procedures Compliance Review Sessions SOP*' for more information.

Quit Attempts During the Study:

At each study visit, we will ask the participant if she is currently abstaining from smoking with the intention of quitting. Although this study is not a treatment program, if a subject quits smoking they will still be able to participate. Subjects who quit smoking may continue to be enrolled in the study and receive compensation even if they are not smoking, as long as they continue study visits and regular monitoring. We will provide subjects endorsing a quit attempt with information about smoking cessation and referrals to local treatment programs. We will also give subjects the option of taking study cigarettes home. Subjects will be under no obligation to smoke these cigarettes, but will still be required to keep track of them, and bring them to the laboratory each visit.

If a Participant is Currently Abstaining from Smoking with the Intention to Quit:

- Encourage participant to continue abstaining from smoking
- Schedule the participant for normal weekly visits.
- Provide the participant with the '*Clearing the Air*' manual and local smoking cessation resources
- Give the participant the option to receive study product rather than require her to take the product
- If the participant chooses to receive the study product have her sign a form acknowledging that cigarette availability could be detrimental to the quit attempt. Recommend that she put the product "away" at home as to avoid unwanted cues to smoke.
- If the participant chooses not to receive the study product, have her contact the lab if she lapses and would like to pick up or be mailed the study product prior to her next visit.

If a Participant is Planning to Quit Smoking, but has not initiated the quit attempt:

- Ask if she has identified a target quit date and, if so, what that target date is
- Provide the participant with the '*Clearing the Air*' manual and local smoking cessation resources
- Provide the participant with the study product as usual. Recommend that on the target date she put the product "away" at home as to avoid unwanted cues to smoke.

Abstinence Assessment Session:

After the week 12 visit, participants will be required to attend one additional visit the following day. Participants will have been encouraged to abstain from smoking leading up to this visit. The abstinence assessment session should be scheduled no less than 18 hours and no more than 30 hours after the Week 12 visit. Abstinence will be verified by CO levels that have decreased by at least 50% from the measure taken during the Week 12 visit. This session will allow us to determine whether the experimental cigarettes have reduced the effects of abstinence on these measures relative to the control conditions. If the participant does NOT meet abstinence criteria, she will only receive \$20 for the visit.

Measures/Assessments

Physiological measures will be collected and entered into REDCap by the interviewer:

- 1) CO
- 2) Blood pressure
- 3) Heart rate

The following assessments will be administered as an interview and will be entered directly into REDCap by the interviewer:

- 1) Concomitant Medications Form
- 2) Health Changes Questionnaire
- 3) Time Since Last Cigarette Questionnaire
- 4) Medical Event Form (if applicable)
- 5) Maintenance Drug Dose Questionnaire (if applicable)

The following assessments will be completed by the participant directly in REDCap:

- 1) BDI
- 2) OASIS
- 3) MNWS
- 4) QSU-brief – with reference to assigned cigarette
- 5) CPT - with reference to assigned cigarette
- 6) CES – Usual Brand Cigarette Version
- 7) COVID-19 Symptom Questionnaire

In the event that the REDCap website is not functioning, the assessments will be administered aloud and participant answers will be recorded securely. The interviewer will enter the data into REDCap when it resumes functioning properly. A note indicating that REDCap was not functioning during the session should be recorded in the 'End of Visit Evaluation Form'.

Participants who do NOT meet abstinence criteria will be required to complete the following assessments:

- 1) CO
- 2) Blood pressure
- 3) Heart rate
- 4) Concomitant Medications Form
- 5) Health Changes Questionnaire
- 6) TLFB
- 7) Medical Event Form (if applicable)
- 8) BDI
- 9) OASIS
- 10) COVID-19 Symptom Questionnaire

Gestational Week 28 Phone Call

Participants who have completed the study prior to week 28 of gestation will have a follow-up phone call at approximately 28-weeks gestation. Researchers will collect smoking patterns in the non-intervention period between completion of the study and giving birth by administering a Timeline Follow Back, which will assess tobacco and nicotine product use during the past 7 days. Participants will be compensated \$25 for completion of this call.

Participant Compensation:

The total amount of money that participants could earn for this study is \$2346 . Participants will receive \$25 for completing the screening visit, plus an additional \$25 bonus for completing the visit on time as scheduled. Payment will be made regardless of enrollment as long as the participant meets the minimum requirements for CO or urinary cotinine levels. Participants will receive \$100 for each of the shorter sessions (Baseline 1, Study Weeks 1, 2, 3, 4, 5, 7, 8, 9, 10, and 11), \$150 for each of the longer sessions (Baseline 2, Weeks 6 & 12), \$40 for biochemical verification of abstinence, \$25 for completion of Gestational Week 28 phone call, up to \$221 for completing daily IVR reports of study cigarette and other nicotine and tobacco use. Participants will also have a chance to earn an additional \$50 bonus for

every three visits that are completed on time as scheduled. There will also be a \$100 bonus for completing the study for a total bonus of \$325. If the participant does not attend the screening visit or one of the weekly visits as scheduled, they will forfeit the bonus. They will have a chance to earn another bonus payment with the next set of three visits. Participants will also have a chance to earn additional money through the Variable Incentive Program. As mentioned above, participants will have a chance to earn additional incentives each month for compliance, honesty and attendance. Participants will be given a debit card at the beginning of the study (during the second portion of the screening visit) and compensation for each visit will be automatically transferred to the card after they complete that visit. If debit cards are unavailable, participants will be paid via an alternate method (i.e. cash or check).

End of Study:

After a participant has completed all study procedures and has been paid for participation the research assistant will read the following script and give the participant the *Clearing the Air Manual*.

"If you've reduced your smoking during this study, we encourage you to continue these reductions or even consider quitting. We would like to provide you with some resources should you decide to try to abstain from smoking (give "Clearing the Air" and hotline information). Please also feel free to consult with your physician and use any medications she deems appropriate. We will call you in approximately 30 days to ask about your smoking since leaving the study. There is no right answer and we know how difficult quitting can be. Please just answer honestly. The call will take less than 5 minutes. Thanks again for your participation."

The following assessments will be administered using REDCap:

- 1) End of Study Questionnaire

30 Day Follow up Phone Call:

Participants will receive a follow-up phone call between 25 and 35 days after the abstinence assessment session to assess their smoking patterns. The phone questionnaire will last less than five minutes. The questionnaire will ask if the participant is still smoking, how much and whether she has attempted to quit smoking since the end of the study. Participants will receive 5 variable incentive program lottery tickets for completing the call as compensation. Those who report abstinence will be invited to complete for biochemical verification and be compensated \$40 for doing so. A urine sample will be collected to test urine cotinine levels. Additionally, any Medical Event Forms that remain open from the last session will be discussed.

Once a participant has completed all study procedures and all open events have been closed, the PI or project manager will review the participant's records and sign a form indicating study completion for that participant.

Birth Outcomes Data

Researchers will collect birth outcome data through review of maternal birth medical records.

Study 2 Randomization

At the end of the Baseline 2 session, participants will be randomized into one of two cigarette conditions. Participants in each condition will be assigned cigarettes that match their menthol preference. Participants will be randomized, using block randomization, in equal number to the dose conditions, with randomization stratified by study site and menthol status. Each site will randomize participants until the total goal of 106 participants across both sites is reached, and no effort will be made to recruit a specific number of menthol and non-menthol smokers at each site.

Condition	TPMF Code	Type*	Specifications Nicotine Yield	Specifications Tar Yield	Specification Range for Nicotine Yield	Specifications Nicotine Content
2	NRC102	RN	0.03 ± 0.01	9 ± 1.5	0.02 - 0.04	0.37 ± 0.01
2	NRC103	RN-Men	0.03 ± 0.01	9 ± 1.5	0.02 - 0.04	0.39 ± 0.00
3	N/A	Usual Brand	N/A	N/A	N/A	N/A
3	N/A	Usual Brand-Men	N/A	N/A	N/A	N/A

*Legend:	
RN	Reduced Nicotine
RN-Men	Reduced Nicotine-Menthol

The lead statistician will create a randomization schedule for each of the two sites, amounting to 150% of expected enrollment at each site. The excess randomization codes will be used in the event that a site will have to enroll extra participants due to unexpectedly slow enrollment at another site.

The University of Vermont will be responsible for assigning product based on the randomization schedule being provided by the UVM Biostatistics Core, and shipping the study cigarettes to each site as needed based on recruitment. Usual brand cigarettes will be purchased by each site as needed. Each site will be responsible for tracking product received and distributed to participants, collecting unused product from participants, and returning unused VLNC cigarettes to UVM.

During weeks 1-12, participants will be provided with a 10-day supply of research cigarettes equivalent to 100% of their smoking rate. This will ensure adequate availability of cigarettes in the numerous locations participants may typically keep a supply (home, work, vehicle, etc.) as well as avoid expending the entire supply if they miss a scheduled visit. Participants will be instructed to use the research cigarettes through Week 12, at which point they are to discontinue product use.

If there is prior knowledge a participant will be missing a visit (i.e. planned vacation, laboratory closure, etc.), then the participant will be provided with an adequate supply of cigarettes to make up for the missed visit(s).

Participants will be asked to refrain from use of other non-study cigarettes during the study period. However, they will be told there is not a penalty for use of non-study cigarettes, and that it is crucial for them to report any use of non-study cigarettes or other nicotine or tobacco products. Throughout the baseline and experimental periods, an Interactive Voice Response (IVR) system will be used on a daily basis to record the number of study cigarettes and non-study cigarettes used the previous day. During the baseline and first experimental week, participants will also answer daily IVR questions about their mood. Participants will be seen weekly for assessments. Brief standardized review sessions focusing on compliance with the study cigarettes and other study procedures will be provided at each visit.

Product Accountability:

Participants will be required to keep track of all the cigarettes provided to them. Therefore, they will be instructed to return all unused cigarettes and empty cigarette packs to the laboratory each week. Research staff will complete the 'Product Accountability Log' as they process participants' products. Any discrepancies in the product dispensed versus product returned will be discussed and recorded in the log. Empty cigarette packs will not be saved; however, research staff will keep all empty cartons in storage for reference. Unused cigarettes will be re-distributed to the participants during Weeks 1-12. Any remaining unused cigarettes returned by the participants will be collected by the research staff.

If participants lose more than two packs of cigarettes and require an unscheduled visit to the laboratory to supplement their supply, they will be told the next time they lose more than two packs they will have to wait until their next scheduled appointment to receive more cigarettes.

Study 2 Statistical Methods and Sample Size

Continuous outcomes will be summarized by the mean, standard deviation, median and range. Categorical outcomes will be summarized by frequencies and percentages. Skewed continuous outcomes will be log- or square-root transformed as appropriate. Variables measured at each baseline visit will be averaged and the average will be used as the baseline measurement. As we expect conditions will be balanced on important baseline characteristics due to randomization, our primary analysis for all endpoints will not be adjusted for potential confounders. However, a secondary analysis will be completed for all outcomes adjusting for demographic characteristics (e.g., age) that we found to be important in prior studies. Potential moderators such as obesity (BMI above or below 30) will be explored by adding that term to the model and the moderator-by-condition term to the model.

